5.4 Statistical models

5.4.1 Primary analysis

Responses will be summarized in terms of percentage rates with 90% CIs. An exact binomial confidence interval (implemented using SAS procedure FREQ with EXACT statement for one-way tables) will be calculated ([Clopper and Pearson, 1934](#)).

SAS procedure FREQ will be used to estimate the proportion of responders, along with the associated 90% ($=100 \times (1 - \text{two-sided alpha level})$) two-sided Pearson-Clopper CI.

5.4.2 Key secondary analysis

Kaplan-Meier estimates

For time to event endpoints (time to response, duration of response etc..), an estimate of the survival function will be constructed using Kaplan-Meier (product-limit) method as implemented in PROC LIFETEST with METHOD=KM option.

Quartiles of the survival function, if reached, will be obtained along with 90% confidence intervals calculated from PROC LIFETEST output using the method of ([Brookmeyer and Crowley, 1982](#)). Kaplan-Meier estimates of the survival function with 90% confidence

intervals at specific time points will be summarized. The standard error of the Kaplan-Meier estimate will be calculated using Greenwood's formula ([Collett, 1994](#)).

6 Reference

1. Clopper CJ and Pearson ES (1934). The use of confidence or fiducial limits illustrated in the case of the binomial. *Biometrical*, 26, 404-413.
2. Brookmeyer R and Crowley J (1982). A Confidence Interval for the Median Survival Time. *Biometrics*, 38, 29 - 41.
3. Collet D (1994). Modelling survival data in medical research. London, Chapman & Hall.

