## 1.2 Purpose

The most important advancement in refractory and relapsed SAA treatment in the past few decades has come from the seminal observation that a thrombopoietin (TPO) receptor agonist, eltrombopag, has activity in SAA. This was demonstrated in a phase I/II study (Study number: ETB115AUS28T) at the US National Institutes of Health where a remarkable 40% of patients' refractory to IST showed hematologic response to this single oral agent ([Desmond et al 2014](#)). Thrombopoietin is the principal endogenous regulator of platelet production. In addition, TPO also has stimulatory effects on more primitive multilineage progenitors and stem cells in vitro and in animal models. Given the mechanism of action of eltrombopag and the presence of the cognate receptor (c-mpl) in primitive elements of the bone marrow, it is possible that this drug stimulates very early progenitors given, in some cases, the marked improvement of all 3-cell lineages in SAA patients.

Efficacy and safety of eltrombopag in refractory SAA patients of East Asian has been confirmed by a non-randomized, open-label, phase II Japanese study (Study number: ETB115E1201), showing a similar response in Japanese subjects, with 47.6% response rate reported at Week 26 following treatment with eltrombopag, with multilineage hematologic responses observed. In this study, eltrombopag up to a dose of 100 mg/day was associated with a safety profile generally as expected for treatment with eltrombopag and in this Japanese subject population (20 subjects). Safety of eltrombopag in Chinese patients has been demonstrated in a randomized phase III study comparing the efficacy and safety of eltrombopag with placebo in Chinese patients with immune thrombocytopenia, where good tolerability was shown, with a similar profile compared to that in western population and no new safety signals identified in Chinese patient population.

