Following the response assessment at Week 26, if all of the hematologic response criteria (i.e. platelet count  $> 50 \times 10^9/L$ , hemoglobin level  $> 100 \text{ g/L}$  without transfusion, and neutrophil count  $> 1.0 \times 10^9/L$ ) remain fulfilled for more than 8 weeks, the dose of eltrombopag will be decreased by half. If the responses continue for further 8 weeks even at the decreased dose, the treatment will be discontinued. If a decrease in any of the hematologic values (i.e. platelet count  $< 30 \times 10^9/L$ , hemoglobin  $< 90 \text{ g/L}$ , or neutrophil count  $< 0.5 \times 10^9/L$ ) is found after dose reduction, the dose may be increased to the previous level. Furthermore, after treatment interruption, the treatment may be restarted if any of the hematologic values decreases to the above mentioned levels. The rationale for tapering eltrombopag after 6 months treatment and permitting dose interruption is listed below:

- In the ETB115AUS28T study, subjects who achieved the 'trilineage haematopoiesis' criteria (defined as platelet count  $> 50 \times 10^9/L$ , hemoglobin level  $> 100 \text{ g/L}$  without transfusion, and neutrophil count  $> 1.0 \times 10^9/L$  for more than 8 weeks) tapered off of eltrombopag in 75 mg decrement every 8 weeks provided criteria continued to be met. Five subjects were tapered off of eltrombopag treatment after meeting these criteria; none of these five subjects have subsequently relapsed, with median follow-up duration of 20.6 months. These data support the current study dosing guidelines.
- In the ETB115AUS28T study, seven subjects have tapered off (n=5; due to 'tri-lineage hematopoiesis'), or discontinued (n=1; AE leading to withdrawal; n=1 cytogenetic abnormality) treatment with eltrombopag and have maintained their response after discontinuation of eltrombopag with no additional treatment for SAA. The subject discontinuing due to AE (leading to withdrawal) continued to have improvement in platelet, ANC as well as hemoglobin values after eltrombopag discontinuation without any additional therapy for SAA. The subject who discontinued treatment due to cytogenetic abnormality continued to have improvements in platelet count, haemoglobin and ANC values at the last study visit, 9 months after the last dose of eltrombopag.

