2.7.2 Statistical hypothesis, model, and method of analysis

Hematological Response at Week 13 and Week 52

The number and percentage of subjects who meet the hematological response criteria (at Week 13 and Week 52 respectively) will be presented and exact 90% confidence interval will be reported. And the number and percentage of assessment item for the hematological response criteria and for the detailed hematological response criteria will be presented.

The derived response by programming at week 13 and Week 52 will also be summarized as above.

Changes in platelet count, hemoglobin and neutrophil count

Values and changes in platelet count (in the absence of platelet transfusion), hemoglobin (in the absence of RBC transfusion) and neutrophil count (in the absence of G-CSF) will be summarized at each visit. Descriptive statistics including mean, SD, median, 25th and 75th percentiles, minimum, and maximum will be summarized for the changes.

Median and interquartile range will be plotted.

Time to hematological response

The distribution function of time to hematologic response will be estimated using the Kaplan-Meier method and will be plotted. The median time to hematologic response along with 90% CIs will be presented. If a subject does not meet hematological response before or at the cutoff date, censoring will be performed using the date of the last assessment.

Duration of hematological response

The distribution function of duration of hematologic response will be estimated using the Kaplan-Meier method and will be plotted. If the number of relapses or deaths allows, the median time to hematologic response along with 90% CIs will be presented.

Relapse-free probability will be estimated using the Kaplan-Meier method at 3 months, 6 months, 9 monthes, one year, and yearly after as well.

Frequency and amount of transfusion

The frequency and the amount of platelets transfusion in each period (Baseline: 4 weeks before Day 1; Week 13, 26, 52: 4 weeks before each visit day) will be summarized by descriptive statistics including mean, SD, median, 25th and 75th percentiles, minimum, and maximum.

Proportion of subjects with transfusion decrease

The number and percentage of subjects with platelet or RBC transfusion decrease or transfusion-free in each period will be presented.

In addition, the number and percentage of subjects with 50% platelet or RBC transfusion reduction in each period will be presented.

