2.14 Interim analysis

There will be no formal interim analysis planned in this study.

3 Sample size calculation

As this is a bridging study to support China registration, an estimation strategy rather than formal hypothesis testing will be pursued. Approximately 20 subjects will be enrolled into the study based on the feasibility rather than statistical considerations. This number of subjects is considered appropriate to assess the efficacy and safety of eltrombopag in Chinese patients.

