3.1 Primary analysis

The hematologic response rate at Week 24 in the pivotal study of NIH-09-H-0154 was 40%. Assuming a same response rate (40%) in Chinese subjects, the 90% confidence interval of the hematological response rate with a total of 20 subjects will be (21.7%, 60.6%).

Below table shows the 90% CIs for various observed response rate. The maximum half-width of the 90% CIs is 19.8%.

Table 3-1 90% CIs for various observed response rate

Sample size	# of responders	Hematologic response rate (%)	90% CI (%)
20	4	20	(7.1, 40.1)
20	6	30	(14.0, 50.8)
20	8	40	(21.7, 60.6)

Sample size	# of responders	Hematologic response rate (%)	90% CI (%)
20	10	50	(30.2, 69.8)

The 12 evaluable subjects for intensive PK sampling was chosen based on feasibility and practical considerationzs to assist in characterizing the PK of eltrombopag in Chinese subjects.

4 Change to protocol specified analyses

No change from protocol specified analysis was made.

5 Appendix

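### At any landmark reached before the first relapse or death, the planned Greenwood interval for the relapse-free probability has zero width or is not produced

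*SAP*

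**What the plan says.** SAP 2.7.2, under duration of hematological response: "Relapse-free probability will be estimated using the Kaplan-Meier method at 3 months, 6 months, 9 monthes, one year, and yearly after as well". SAP 5.4.2 adds the intervals, "Kaplan-Meier estimates of the survival function with 90% confidence" limits at specific time points, and fixes the variance: "The standard error of the Kaplan-Meier estimate will be calculated using Greenwood's formula". The Brookmeyer-Crowley method is named for quartiles only. No transformation (plain, log-log or other) is named for the landmark intervals, and there is no rule for a landmark with no events.

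SAP 2.7.1 restricts the analysis to responders with at least two response assessments. It counts loss of the response criteria, or death, as the event. It asks for the analysis for overall response and separately for platelets, hemoglobin and neutrophils. Duration of response is one of the efficacy analyses to be generated for the final CSR.

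On size, SAP section 3 says: "Approximately 20 subjects will be enrolled into the study based on the feasibility rather than statistical considerations". SAP 3.1 plans on a 40% response rate.

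**The concern.** A Greenwood interval is a large-sample device whose width comes only from events already seen. Here it is applied to perhaps 8 to 10 subjects, and to fewer in a single-lineage set. If the first landmarks pass without an event, following the plan as written gives an estimate of 100% with limits of 100% and 100%, or a blank.

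The first output would present complete certainty from a handful of subjects. The second would leave durability without any statement of precision. The SAP uses an exact interval for the response rate in all 20 subjects, but a large-sample one in roughly half that number. Duration of response is a secondary objective of a bridging study meant to support registration, so a reader may rely on these figures.

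**Working it through.** **Inputs**
- N = 20 and planning response rate 40% (SAP sections 3 and 3.1): 0.40 × 20 = 8 responders.
- Protocol 1.2 reports the Japanese study "with 47.6% response rate reported at Week 26 following treatment with eltrombopag": 0.476 × 20 = 9.5. The top row of SAP Table 3-1, 50%, gives 10. I use n = 8, 9 and 10.
- Confidence level 90% (SAP 5.4.2), taken as two-sided as in SAP 5.4.1, so z = 1.645.
- True relapse-free probability S at a landmark: not in the documents. Assumed range 0.70 to 0.95.

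**Step 1: the plan's own precision figures.** Two-sided 90% Clopper-Pearson limits for n = 20 give 4/20 (7.1, 40.1), 6/20 (14.0, 50.8), 8/20 (21.7, 60.6) and 10/20 (30.2, 69.8), with a maximum half-width of 19.8%. All agree with SAP Table 3-1. No precision is stated for the relapse-free probabilities.

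**Step 2: landmark with no event.** Greenwood: Var = Ŝ² × Σ d/[r(r − d)], summed over event times, with d events among r at risk. With no event the sum is empty, so Var = 0. Plain limits are 100% and 100%. Log-log limits need log(−log 1), which is undefined. This needs no assumption about S or censoring.

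Without earlier censoring, the exact two-sided 90% lower limit is 0.05^(1/n): 68.8% (n=8), 71.7% (n=9), 74.1% (n=10). For a single-lineage set of 5, an assumed size, it is 0.05^(1/5) = 54.9%.

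**Step 3: overall coverage without censoring.** The number still relapse-free, x, is Binomial(n, S), Ŝ = x/n, and the Greenwood variance is Ŝ(1 − Ŝ)/n. Coverage is the summed probability of every x whose interval contains S; x = n counts as a miss. P(no event) = S^n, for example 0.90^8 = 0.430.

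| S | P(no event), n=8 / 9 / 10 | n=8: plain / log-log | n=9: plain / log-log | n=10: plain / log-log |
|---|---|---|---|---|
| 0.95 | 66 / 63 / 60% | 33 / 28% | 36 / 30% | 39 / 32% |
| 0.90 | 43 / 39 / 35% | 57 / 53% | 60 / 56% | 64 / 58% |
| 0.85 | 27 / 23 / 20% | 71 / 62% | 73 / 73% | 79 / 75% |
| 0.80 | 17 / 13 / 11% | 78 / 78% | 85 / 78% | 86 / 86% |
| 0.75 | 10 / 8 / 6% | 87 / 79% | 88 / 88% | 92 / 87% |
| 0.70 | 6 / 4 / 3% | 88 / 88% | 78 / 86% | 80 / 92% |

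Clopper-Pearson covers 92-99% over the same grid. A simulation (20,000 runs, n = 8 and 10) with 20% censored by the landmark gives 48-60% at S = 0.90, 74-84% at 0.80 and 81-89% at 0.70.

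**Step 4: where the loss comes from.** Coverage given at least one event is total coverage divided by 1 − S^n.
- S = 0.90, n=8: 0.565/0.570 = 99% (plain) and 0.531/0.570 = 93% (log-log). For n=10: 0.639/0.651 = 98% and 0.581/0.651 = 89%.
- S = 0.80, both scales: 0.776/0.832 = 93% (n=8) and 0.860/0.893 = 96% (n=10).
- Weak spots: log-log at S = 0.95, 83% (n=8) and 79% (n=10); plain at S = 0.70, 0.779/0.960 = 81% (n=9) and 0.803/0.972 = 83% (n=10).

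**Step 5: one relapse in 8.** Ŝ = 0.875 and SE = √(0.875 × 0.125/8) = 0.117. Plain: 0.875 − 1.645 × 0.117 = 68.3%, up to 100% after truncation. Log-log: 50.0% to 97.5%. Exact: 52.9% to 99.4%.

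**The case against.** Greenwood intervals are conventional, the trial tests no hypothesis, no decision rule uses these landmarks, and the primary endpoint already has an exact interval. The SAP shows some awareness of sparse events, since it gives the median only if the number of relapses or deaths allows. A blank at a zero-event landmark is not false certainty, yet the coverage figures score it as a miss. All of this stands and limits the consequence. It does not supply the missing rule: the median's condition does not extend to the landmarks, and the SAP does not say what will be displayed.

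A reader might also infer three stronger things that the documents do not support.

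- *That true coverage is far below 90% in general.* S is not given. Coverage is far below 90% when S is about 0.85 or higher, but 78-92% at 0.70-0.75.
- *That intervals after one or two relapses are far too narrow.* Given at least one event, coverage is 79-99% over the grid and mostly near or above 90%. With one relapse in 8 the log-log interval is about as wide as the exact one. The plain lower limit is too high there (68.3% against 52.9%), which is a reason to name the scale.
- *That zero-event landmarks are likely because the earlier US study saw none.* Protocol 4.2.1 does say "none of these five subjects have subsequently relapsed", but those subjects were tapered because they had met trilineage criteria. Here any single-lineage response qualifies and any loss of the response criteria counts as relapse, so S could be lower.

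The figure of 8 to 10 is an expectation. Responses at other visits could raise it, and the two-assessment rule could reduce it.

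**Conclusion.** The point holds for landmarks reached before the first relapse or death. There the prescribed variance is 0, and the plan yields a zero-width interval or none, where about 69% (n=8) to 74% (n=10) is the exact lower limit without earlier censoring. That result follows from the formula alone. The coverage figures rest on an assumed S, an expected responder count, no earlier censoring, and counting a zero-event landmark as non-coverage. For n = 8 to 10 coverage runs from 28-39% at S = 0.95, through 62-79% at 0.85, to roughly nominal or modestly low at 0.70-0.75. From S = 0.80 upward most of the non-coverage is the zero-event case. At 0.70 the shortfall is small to moderate and has other sources. The output is a descriptive secondary one, so this should be corrected but does not threaten the main result.

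**What to change.** Keep the Kaplan-Meier point estimate. In SAP 5.4.2 and 2.7.2, replace the Greenwood interval at the landmarks by an exact-type small-sample interval. The beta product confidence procedure is one choice; it equals Clopper-Pearson when nobody is censored before the landmark. At minimum, state that a zero-event landmark gets an exact-type lower limit based on the number at risk, and name the transformation used at all other landmarks. In either case print the number at risk beside each landmark, for overall response and for each lineage.

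The cost is SAP wording, a short validated macro outside the planned PROC LIFETEST output, and wider intervals. No data collection or trial conduct changes.
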